2.3 Overview of Study Design

We will undertake a prospective cohort study among subjects with heart failure seen at one of two sites: (1) Columbia University Irving Medical Center and affiliated ColumbiaDoctors sites and (2) Allen Hospital of NY Presbyterian. Patients identified as having a high probability of having undiagnosed cardiac amyloidosis will undergo comprehensive cardiovascular examinations including: (1) complete medical history documenting the presence of HF and any symptoms that could be associated with cardiac amyloidosis, as well as any additional co-morbid conditions or symptoms, (2) targeted physical exams including orthostatic blood pressure measurements, assessment for gallops and volume status (e.g. JVP, rales, edema) and determination of functional class, (3) standard 12 lead electrocardiogram, (4) full two-dimensional and three-dimensional echocardiograms with Doppler flow assessment and tissue Doppler and speckle tracking (See procedures for details), (5) cardiac amyloid scintigraphy, and (6) blood testing for monoclonal protein testing.

2.3.1 Patient Recruitment

The CAD-Trial study is designed to identify a sufficient number of cases to prospectively validate that deep learning models can detect undiagnosed cardiac amyloidosis in large populations of patients undergoing cardiac testing. To accomplish this objective, we will undertake an approach to cohort

identification and selection is used that deliberately selects for subjects who are at increased risk for cardiac amyloidosis.

Patient Recruitment: To accomplish the above objectives, the cohort will be identified by examination of all patients who had an ECG and echocardiogram at CUIMC within the last 5 years (Figure 3). The deep learning model will be applied to this dataset of patients to create a list of patients at highest probability of having cardiac amyloidosis. The medical records of these patients will be evaluated for inclusion and exclusion criteria, and the 100 highest probability patients who agree to take part in the study will be enrolled.

Selection criteria: 100 patients will be enrolled in this protocol. *Inclusion criteria* will include age \geq 50 years, electronically stored ECG and echocardiogram within 5 years of study start date, ability for the patient or health care proxy to understand and sign the informed consent after the study has been explained. *Exclusion criteria* include a previous diagnosis of ATTR, AL, or AA amyloidosis, previous testing for cardiac amyloidosis such as a prior cardiac amyloid scintigraphy, cardiac, or fat pad biopsy, prior organ transplantation, active malignancy, or non-amyloid heart disease with an expected survival of less than one year.

Study procedures: Eligible patients will be identified in the manner above and invited to participate in the study by phone call. During this phone call, they will be assessed for eligibility and undergo an informed consent process. A study visit will then be scheduled. At the study visit, they will undergo a history and physical examination by a physician, 12 lead electrocardiogram, transthoracic echocardiogram, blood testing for monoclonal proteins, blood biobanking, and cardiac amyloid scintigraphy. They may be offered TTR genetic testing by blood or saliva sample if preliminary testing is concerning for amyloidosis, counseling on that decision, and given the choice of whether to have genetic testing without it affecting their ability to participate in the other study procedures. Patients will be given a \$100 debit card for their participation in the study and will be provided a car service if needed and feasible for transport to and from the study site. After completion of all testing, patients will be counseled on the findings of their testing and appropriate referrals for follow-up or further testing will be made. For the purposes of the study, a diagnosis of cardiac amyloidosis will be made in the following settings:

[figure not shown]

Figure 3: Study Flow. This diagram demonstrates the analysis of patients and data with the goal of performing 99mTc-PYP scanning on 100 patients identified by our deep learning model to be at high probability of having undiagnosed ATTR-CA.

- ATTR-CA diagnosis: A diagnosis of ATTR-CA will be made according to consensus guidelines by an amyloidosis expert.^{18, 19} These includes imaging criteria with requires that a patient's cardiac amyloid scintigraphy SPECT scan shows myocardial uptake and follow-up monoclonal protein testing shows no evidence of AL amyloidosis or pathologic criteria with a biopsy showing ATTR.
- AL-CA diagnosis: A clinical diagnosis of AL-CA will be by an amyloidosis expert according to society guidelines. These includes a diagnosis made in one of the following settings: (1) cardiac biopsy showing AL deposition and (2) extra-cardiac biopsy showing AL deposition with typical cardiac features on imaging including echocardiography or cardiac magnetic resonance imaging.

2.3.2 Study Procedures

The timing of all procedures in this study is outlined in Table 4. Eligible patients will be identified. Patients who are interested in the study will have a screening visit to evaluate for eligibility and obtain informed consent. If patients qualify for study and do consent they will have their study visit within 4 weeks of screening. At that visit they will have all of the following testing done.

Table 4. Study Procedures

Procedure	Screening (phone visit)	Baseline	Phone wrap-up visit
Informed Consent	X		
Inclusion and Exclusion Criteria	X		
Baseline History		X	
Height and Weight [‡]		X	
Vitals Signs		X	
Medications		X	
Clinical Examination		X	
Adverse Events Review		X	
Blood draw for monoclonal protein testing, genetic testing, and biobanking		X	
Electrocardiogram		X	
Echocardiogram		X	
^{99m} Tc-PYP administration		X	
^{99m} Tc-PYP Scintigraphy		X	
Patient compensation - \$100 debit card		X	
Phone Call Follow-Up			X

Appropriate referral for follow-up in the event of ATTR-CA diagnosis or discovery of other serious pathology			X
--	--	--	---

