CLINICAL STUDY PROTOCOL

Cardiac Amyloidosis Discovery Trial
(CAD Trial)

ClinicalTrials.gov ID: NCT06469372

Protocol Version: 7.0

Protocol Date: August 22, 2024

Sponsor affiliation: Columbia University Medical Center
Clinical Cardiovascular Research Laboratory for the
Elderly (CCRLE)
[name]
[name]

Sponsor-Investigator: [name]
Principal Investigator

STUDY SYNOPSIS

Protocol Title	Cardiac Amyloidosis Discovery Trial (CAD-Trial)
Protocol Number	7.0
Design	
This is a single center, diagnostic clinical trial in which we aim to prospectively validate a deep learning model that identifies patients with features suggestive of cardiac amyloidosis, including transthyretin cardiac amyloidosis (ATTR-CA). Cardiac Amyloidosis is an age-related infiltrative cardiomyopathy that causes heart failure and death that is frequently unrecognized and underdiagnosed. We have developed a deep learning model that identifies patients with features of ATTR-CA and other types of cardiac amyloidosis, including echocardiographic, ECG, and clinical factors. By applying this model to the entire Columbia University Irving Medical Center's patient population, we will identify a list of patients at highest predicted risk for having undiagnosed cardiac amyloidosis. We will then invite these patients for further testing to diagnose cardiac amyloidosis with the goal of recruiting 100 total patients.
 
Consented eligible patients will be evaluated for the presence and clinical manifestations of cardiac amyloidosis. Patients will undergo a single study visit, using amyloid nuclear scintigraphy, monoclonal protein testing and a physical examination. Those who meet criteria for the disease will be given the diagnosis of cardiac amyloidosis. Patients will be counseled on the results of their test findings and appropriate referrals made for further care.

Study Sites	This study is to be conducted at NYP Milstein Hospital and [name] Clinical Cardiovascular Research Laboratory for the Elderly location.
Time on Study	The duration of patient participation in this study is 1 day.
Primary Objective	To prospectively validate a deep learning model to diagnose cardiac amyloidosis, an underdiagnosed, lethal, and treatable cause of heart failure.
Target Sample Size	100 patients

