Inclusion and Exclusion Criteria	
Every participant must meet all of the following inclusion criteria to be eligible for enrollment in this study:
 
 1. High predicted probability of having cardiac amyloidosis as determined by deep learning model 2. Age \geq 50 years 3. Electronically stored ECG and echocardiogram within 5 years of study start date

	
4. Ability for the patient or health care proxy to understand and sign the informed consent after the study has been explained.
 
Exclusion criteria
 
 1. Primary amyloidosis (AL) or secondary amyloidosis (AA). 2. Prior liver or heart transplantation. 3. Active malignancy or non-amyloid disease with expected survival of less than 1 year. 4. Previous testing for cardiac amyloidosis such as amyloid nuclear scintigraphy, cardiac, or fat pad biopsy 5. Impairment from stroke, injury or other medical disorder that precludes participation in the study. 6. Disabling dementia or other mental or behavioral disease. 7. Enrollment in a clinical trial not approved for co-enrollment. 8. Inability or unwillingness to comply with the study requirements. 9. Nursing home resident. 10. Other reason that would make the subject inappropriate for entry into this study.
Aims	
The specific aims of this investigation include:
 
 1. To prospectively validate that deep learning models can detect undiagnosed cardiac amyloidosis in large populations of patients who have undergone cardiac testing. 2. To incorporate additional data to improve the deep learning model's detection of cardiac amyloidosis.
Safety Assessments	
The safety of study participants will be evaluated by:
 
 1. Assessment of adverse events (AEs), including serious adverse events (SAEs). 2. Vital sign measurements (blood pressure, pulse rate, and respiratory rate). 3. 12-Lead electrocardiogram (ECG). 4. Physical examinations 5. Echocardiography

LIST OF ABBREVIATIONS AND DEFINITIONS OF TERMS

Abbreviation or Specialist Term	Explanation
99mTc-PYP	99mTechnetium pyrophosphate
99mTc-HMDP	99mTechnetium hydroxymethylene diphosphonate
AE	Adverse event
AI	Artificial Intelligence
TTR	Transthyretin
AL-CA	Light chain cardiac amyloidosis
ATTRm	Mutant Transthyretin amyloidosis
ATTRwt	Wild-type Transthyretin amyloidosis
ATTR-CA	Transthyretin cardiac amyloidosis

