2.3.2.2 Cardiac amyloid scintigraphy

A nuclear medicine technologist will perform planar cardiac imaging of the chest using dual-headed gamma cameras equipped with low energy, high resolution collimators. 10-25 mCi of ^{99m}Tc-PYP or 10-20 mCi of ^{99m}Tc-HMDP will be administered intravenously and imaging will be performed after approximately 3 hours. The anterior and lateral planar views centered on the heart will be obtained simultaneously for a total of at least 750K counts/view (approx. 3-8 min of imaging). Cardiac retention will be assessed by both a semi-quantitative visual score (range: 0 [no uptake] to 3 [uptake greater than rib]) and a quantitative heart-to-contralateral (H/CL) ratio of total counts in a region of interest (ROI) over the heart divided by background counts in an identical size ROI over the contralateral chest including soft tissue, ribs, and blood pool. A visual score 2 or greater and/or calculated H/CL ratio 1.3 or greater, with myocardial retention of tracer confirmed in all cases by SPECT imaging with or without a CT scan for image registration, will be required to indicate TTR-CA according to prior published data.²⁸ The details of the imaging procedures for cardiac amyloid scintigraphy imaging are shown in Table 5. Each cardiac amyloid scintigraphy scan will be read by a board-certified nuclear cardiologist blinded to clinical information.

Table 5

Imaging procedures	Parameter
Preparation	No specific preparation. No fasting required.
Scan	Rest scan
Dose of ^{99m} Tc-PYP	10-25 mCi intravenously
Dose of ^{99m} Tc-HMDP	10-20 mCi intravenously
Time between injection and acquisition	3-hour planar and optional SPECT
Imaging parameters	
Field of view	Recommended: cardiac or chest; Optional: whole body planar
Image type	Recommended: cardiac or chest SPECT and planar imaging

Position	Supine
Energy window	140 keV, 15-20%
Collimators	Low energy, high resolution
Matrix	64 x 64 minimum

Pixel size	3.5-6.5 mm
Planar imaging specific parameter	
Number of views*	Anterior, lateral, and left anterior oblique
Detector configuration	90 degrees

Image duration (count based)	750,000 counts
Magnification	1.46
SPECT imaging specific parameters	
Angular range	360 degrees
Detector configuration	180 degrees

ECG gating	Off; nongated imaging
Number of views/detector	40
Time per stop	30 seconds
Magnification	1.0

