2.3.2.6 Follow-Up Protocol

Participants will be called after the completion of testing by an investigator to counsel them on the results of their testing. In the event that they are diagnosed with cardiac amyloidosis or are found to have other serious pathology, the following steps will be taken:

- The patient will be told the results of their testing and an appropriate referral for follow-up made. If the patient has a treating physician, they will be instructed to go to their physician for further care as needed. In the event of an amyloidosis diagnosis, the patient will be referred to the Columbia University Amyloidosis Center for further care. If they do not have a treating physician, they will be given an appropriate referral for further care.
- A letter will be generated and mailed to the patient and uploaded to the patient's medical record. This letter will state the results of their testing and recommend that the patient see a physician for further care.

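### Adverse events are reviewed only at the baseline visit, and the wrap-up call already planned for participants asks nothing about them, so events starting after the visit are not systematically recorded.

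*Combined protocol and SAP*

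**What the plan says.** Section 2.3.2 gives its table authority over timing: "The timing of all procedures in this study is outlined in Table 4". The table has three columns: phone screening, baseline and a phone wrap-up visit. The row "Adverse Events Review" carries a single mark, under baseline. The wrap-up column is marked for two rows only, "Phone Call Follow-Up" and referral where ATTR-CA or other serious pathology is found.

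Section 2.3.2.6 describes the call: "Participants will be called after the completion of testing by an investigator to counsel them on the results of their testing". This covers participants in general. The further steps listed there apply to those with amyloidosis or other serious findings, and none of them concerns adverse events.

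The synopsis puts this first among its safety assessments: "Assessment of adverse events (AEs), including serious adverse events (SAEs". It gives no start or end for collection. Under time on study it states: "The duration of patient participation in this study is 1 day".

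On exposure, section 2.3.2.2 has an intravenous tracer given at the visit and says that "imaging will be performed after approximately 3 hours". Blood is drawn at the same visit. On size, section 2.3.1 says that "100 patients will be enrolled in this protocol".

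**The concern.** The plan commits to assessing AEs and SAEs, exposes each participant to an injection and a blood draw, and then looks for events only during that visit. It also schedules a later conversation between an investigator and the participant, which is the natural moment to ask, and does not use it for this.

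What is at stake is how complete the safety data are, and what a safety statement from this trial would mean. If the trial reported no adverse events, a reader could not tell from the protocol that the period covered was essentially the hours of one visit. A serious event in the following days would enter the record only if the participant volunteered it and someone chose to write it down.

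**Working it through.** No formula applies. The documents give no adverse event rate, collection window or safety sample-size figure, so there is nothing to reproduce. The check is a comparison of the schedule with the text.

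1. **Contacts in Table 4, and whether AE review is marked**
   - Phone screening: no.
   - Baseline visit: yes.
   - Phone wrap-up: no.

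   AE review is therefore marked at 1 of 3 contacts. Screening comes before any study exposure, so the cell that matters is the wrap-up one.

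2. **Who receives the call.** Section 2.3.2.6 addresses participants without restricting the call to those with a positive result. The conditional steps come after that sentence. A post-visit contact is thus planned for the cohort generally, not for a subset.

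3. **What the call contains.** Its stated content is counselling on results and, where needed, referral. Neither Table 4 nor section 2.3.2.6 adds a question about adverse events.

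4. **What period the baseline review can cover.** Tracer injection, imaging about 3 hours later and blood draw all fall at the baseline visit. A review marked there covers hours after exposure.

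5. **Whether another route exists.** The supplied text contains no AE definition, no AE or SAE reporting period, and no other mechanism for capturing events after the participant leaves.

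6. **Whether the 1-day statement defines the window.** It fits visit-day review. It does not fit the rest of the schedule: section 2.3.2 allows up to 4 weeks between screening and the study visit, and a call follows once testing is complete. The statement describes the visit rather than the period of contact, and it does not mention adverse events.

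Taken together, a site that follows the plan exactly would ask about adverse events at the visit and not again, although it speaks to participants afterwards.

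**The case against.** The strongest reply is that visit-day review suits this study. Participation is stated as 1 day. The participant has one diagnostic tracer injection, a blood draw, an ECG and an echocardiogram, with no study treatment and no repeat exposure. No aim or hypothesis concerns safety. The synopsis promises AE assessment without naming a window, so Table 4 does not breach it. This stands as far as it goes: there is no contradiction with a stated objective, and the point is a modest improvement. It does not remove the gap, because the protocol itself schedules a contact after the visit and leaves it unused for safety.

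A second reply is that participants may mention events on the call and nothing prevents recording them. That is correct. A reader might infer from Table 4 that every event after the visit is lost, but the documents do not support this. They show only that nobody is required to ask or record.

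A third reply is that safety text may exist elsewhere. The supplied text passes from section 2.3.3 to section 5, the section numbering is irregular, and Table 4 is not complete in every respect: it names only one of the two tracers that section 2.3.2.2 permits. Safety-reporting text outside what was supplied cannot be ruled out. If it exists, Table 4 should still agree with it, since the table is said to set all timing.

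A fourth reply is that a mark in the wrap-up column does not by itself create a defined window, because the call has no stated timing beyond following completion of testing. This is right, and the fix has to deal with it.

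**Conclusion.** The point holds for the documents as supplied. AE review is scheduled at the baseline visit only, the wrap-up call has no adverse event item, and AEs and SAEs starting after the visit are therefore not systematically asked about or recorded.

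Its size cannot be put as a number of events, because the documents give no rate from which later events could be estimated. A reader might be tempted to measure the gap by the confidence limit for zero events among 100 participants. That limit would be the same whatever window was used, so it says nothing about what is lost by not asking on the call.

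The consequence is limited to the completeness and interpretability of safety data. The primary hypothesis, that at least 20% of those scanned will be diagnosed, is untouched. This is a cheap improvement of low severity. It rests on two assumptions: that the column positions in Table 4 are as they appear in the text, and that no safety-reporting section exists beyond the text supplied.

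**What to change.** - Mark adverse event review in the phone wrap-up column of Table 4, and add it to section 2.3.2.6 as part of the call.
- Ask one short scripted question about any AEs and SAEs since the visit, with a form field for the answer.
- State the AE and SAE collection period as running from the study visit to the wrap-up call, and record the date of the call so that each participant's period is known.
- Report visit-day and post-visit events separately.
- Reconcile the synopsis statement of 1-day participation with the three-contact schedule.

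Cost: about a minute per call, which is an assumption and not a figure from the documents. Over 100 participants that is 100 × 1 = 100 minutes in all, plus one table mark and one form field. The downside is that some background illness will be recorded, and without a comparator group it cannot be separated from effects of the procedures. Reporting the two periods separately makes this visible but does not resolve it.

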2.3.2.1 Clinical Examination

A detailed health investigation will be performed in all patients by a provider experienced in the care of patients with HF. This will include a medical history focused on the presence of HF as defined by standard clinical criteria (NHANES²⁶ and European Society of Cardiology²⁷ for HFpEF), etiology of HF, and co-morbid conditions; physical examination including vital signs, volume status, cardiopulmonary examinations and neurologic examination with focus on neuropathic findings. Exams will take ~45 minutes.

2.3.2.2 Cardiac amyloid scintigraphy

A nuclear medicine technologist will perform planar cardiac imaging of the chest using dual-headed gamma cameras equipped with low energy, high resolution collimators. 10-25 mCi of ^{99m}Tc-PYP or 10-20 mCi of ^{99m}Tc-HMDP will be administered intravenously and imaging will be performed after approximately 3 hours. The anterior and lateral planar views centered on the heart will be obtained simultaneously for a total of at least 750K counts/view (approx. 3-8 min of imaging). Cardiac retention will be assessed by both a semi-quantitative visual score (range: 0 [no uptake] to 3 [uptake greater than rib]) and a quantitative heart-to-contralateral (H/CL) ratio of total counts in a region of interest (ROI) over the heart divided by background counts in an identical size ROI over the contralateral chest including soft tissue, ribs, and blood pool. A visual score 2 or greater and/or calculated H/CL ratio 1.3 or greater, with myocardial retention of tracer confirmed in all cases by SPECT imaging with or without a CT scan for image registration, will be required to indicate TTR-CA according to prior published data.²⁸ The details of the imaging procedures for cardiac amyloid scintigraphy imaging are shown in Table 5. Each cardiac amyloid scintigraphy scan will be read by a board-certified nuclear cardiologist blinded to clinical information.

Table 5

Imaging procedures	Parameter
Preparation	No specific preparation. No fasting required.
Scan	Rest scan
Dose of ^{99m} Tc-PYP	10-25 mCi intravenously
Dose of ^{99m} Tc-HMDP	10-20 mCi intravenously
Time between injection and acquisition	3-hour planar and optional SPECT
Imaging parameters	
Field of view	Recommended: cardiac or chest; Optional: whole body planar
Image type	Recommended: cardiac or chest SPECT and planar imaging

Position	Supine
Energy window	140 keV, 15-20%
Collimators	Low energy, high resolution
Matrix	64 x 64 minimum

Pixel size	3.5-6.5 mm
Planar imaging specific parameter	
Number of views*	Anterior, lateral, and left anterior oblique
Detector configuration	90 degrees

Image duration (count based)	750,000 counts
Magnification	1.46
SPECT imaging specific parameters	
Angular range	360 degrees
Detector configuration	180 degrees

ECG gating	Off; nongated imaging
Number of views/detector	40
Time per stop	30 seconds
Magnification	1.0

